RLS patient ascertainment: A standard patient completed RLS diagnostic questionnaire is given to all of the patients at the [name] clinic as part of their routine clinical evaluation not limited to its use in this study. This questionnaire has a sensitivity and specificity of 87% and 94% respectively [11]. The patients identified by the questionnaire as probable RLS will be checked for meeting the inclusion criteria (see below). They will, If they meet criteria, be approached by the research coordinator to consent to this treatment protocol. If they consent then the

18 July 2014

coordinator will assign them a protocol number and will obtain any needed blood samples. The coordinator will review the clinical history with the patient to ensure they meet inclusion criteria. If they qualify as determined by inclusion/exclusion criteria (see below) the coordinator will schedule the patient for both a validated telephone diagnostic interview [12] by an RLS specialist at Johns Hopkins and two treatment times to occur 2 – 7 days apart starting after the interview. If the Hopkins interview confirms the RLS diagnosis the treatments will be given as scheduled. If the Hopkins interview does not confirm the diagnosis of RLS the patients participation in this study will end and routine care will be given.

Randomization. A table randomizing assignment of participants in order entered will be used to determine group placement. Once a patient has been confirmed with RLS by the telephone clinical interview they will be given an appointment for IV treatment. At the time of IV treatment the subject will be assigned to either IV or oral iron treatment based on the order in the randomized table. The randomization will be in 7 blocks of 10 with equal treatments in each block. The nursing staff will follow the randomization table based on the order of the subjects tested. Each subject will be assigned a study number at the time of the IV treatment. The subject data will be evaluated using this study number and not the protocol number assigned by the coordinator at the time the patient consented to the study.

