Any other medical condition that, in the opinion of Investigator, may cause the subject to be unsuitable for the completion of the study or place the subject at potential risk from being in the study, e.g. a malignancy, uncontrolled hypertension, unstable ischemic heart disease, or uncontrolled diabetes mellitus

Study Endpoints for each subject

The following are endpoints for each patient in the study :

1. At evaluation in the clinic at about 6 weeks after the first IV iron treatment.
2. Termination of participation because of significant adverse effect from the IV infusion in the hour observed after the infusion.
3. Significant adverse event after starting the iron treatment and before the 6 week follow-up evaluation that was judged to require ending the study.
4. Subject decision not to continue in the study after the treatment and before the final evaluation.
5. [name] decision that it would be harmful to the patient to continue in the study.
6. Patient is non-compliant with study requirements and [name] judges this non-compliance is enough to significantly alter evaluation of the treatment. (Note that stopping the

18 July 2014

oral medication because of intolerance to the treatment is not considered non-compliance, but rather an outcome for the study. Patients discontinuing oral medication for adverse effects may qualify for repeat IV treatment.)

Duration of subject participation:

Participation will continue for 6 weeks after treatment for the primary study and for 12 months after treatment for the extension study for those responding to the initial treatments or the open label repeated IV treatment.

Early termination of study:

Subjects may terminate the study at any time or maybe terminated from the study for non-compliance or if continuation in the study is judged by [name] to be harmful to the patient. A telephone evaluation will be scheduled when possible at the time of early termination. The reason for the early termination will be noted.

Blood tests obtained:

Iron panel, hemoglobin and hematocrit will be obtained from morning fasting venous samples at screening prior to treatment and at 4 and 6 weeks after the first treatment. About 15 ml of blood will be obtained for these tests

An additional 24 ml of blood will be collected for lymphocytes the day of the first IV treatment before the treatment and again at 6 weeks after the treatment.

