The percentage responding will be evaluated for each drug condition to determine overall effect size at 6 weeks after treatment. This will be calculated for the IRLS scale and the PGI as change from baseline and for the CGI with response determined as much or very much improved (scores of 1 or 2). All scores greater than 2 on the CGI are considered to indicate no significant response. The onset of treatment will be described as the percentage showing much or very much improvement at each of the evaluations and by the change in IRLS score from baseline at each evaluation. The duration of treatment over the 12 month follow up will be described as the percentage of responders and the IRLS change from baseline at each time point for both oral and IV iron. The oral iron treatment will be stopped for all subjects at the 6-week time point.

The outcomes for the oral versus IV treatments at 6 weeks will be compared using a standard unpaired unequal variance t-test for the change in IRLS scores from baseline. The number of responders compared to no-responders will be compared using the Fisher Exact test.

Sample Size

Uncontrolled experience observing IDA patients with RLS indicated that about 80% responded to IV iron (about 1000mg dose) and 50% responded to standard oral iron treatment over 6 to 12 weeks. These percentage outcomes require a sample size of 70 (35 with each treatment) to provide a power of >80% with alpha = 0.05 to test for differences between these treatments. This was considered a reasonable sample to ascertain the effect size of the two treatments and to provide enough positive outcomes to evaluate time course for improvement with treatment and persistence of the treatment effect.

Breaking the blind

The randomization is in cohort blocks of 10, 5 with each treatment. The blind for the form of initial treatment will be broken for every cohort of 10 treated patients after all members of a cohort have completed the study. The blind may also be broken for specific subjects if the treatment information is needed for medical care of the patient.

Concomitant Medication

Permitted Medications

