7. History of multiple allergies
8. Known hypersensitivity to parenteral or oral iron or any excipients in the drug products
9. Previous IV iron treatment for RLS
10. Other iron treatment or blood transfusion within 4 weeks prior to the screening or treatment visit
11. Planned elective surgery during the study
12. Current (past 4 weeks) use of drugs that treat RLS, e.g. opioids, alpha-2-delta anti-depressants, dopaminergic agents (dopamine promoters, dopamine antagonists/blockers)

Any other medical condition that, in the opinion of Investigator, may cause the subject to be unsuitable for the completion of the study or place the subject at potential risk from being in the study, e.g. a malignancy, uncontrolled hypertension, unstable ischemic heart disease, or uncontrolled diabetes mellitus.

The following endpoint were used for the study:

1. At evaluation in the clinic at about 6 weeks after the first IV iron treatment.
2. Termination of participation because of significant adverse effect from the IV infusion in the hour observed after the infusion.
3. Significant adverse event after starting the iron treatment and before the 6 week follow-up evaluation that was judged to require ending the study.
4. Subject decision not to continue in the study after the treatment and before the final evaluation.
5. Physician's decision that it would be harmful to the patient to continue in the study.
6. Patient is non-compliant with study requirements and was judged the non-compliance was enough to significantly alter evaluation of the treatment. (Note that stopping the oral medication because of intolerance to the treatment is not considered non-compliance, but rather an outcome for the study). Patients discontinuing oral medication for adverse effects may qualify for repeat IV treatment.

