Subjects could terminate the study at any time for could be terminated from the study for non-compliance or if continuation in the study was judged by the PI ([name]) to be harmful. Reasons for termination were recorded. 21 patients were terminated or lost to follow-up. Some of these terminations may have been due to hiatuses in the study caused by the untimely death of the principal investigator ([name]) and the untimely occurrence of the COVID pandemic, interfering with patient visits. A list of those terminated or lost to follow-up are reported in Table _____. As a result, an additional 30 patients were accrued above the planned prespecified number, to achieve appropriate statistical power.

There were two co-primary outcome measures: Clinician Global Inventory-Improvement (CGI-I) assessment at week 6 and the change-in-baseline at 6 weeks in International RLS Study Group Severity Scale (IRLS) score. The Patient Global Inventory-Severity (PGI-S) was a secondary outcome measure (PGI-S). The IRLS and PGI-S were obtained at the clinic visits and at each telephone evaluation, while the CGI-i was only obtained at the Week-6 study endpoint.

Statistical analysis

Baseline and follow up laboratory values were described overall and within each study group. Means and standard deviations and medians and ranges were produced for continuous variables, and frequency counts and percentages were generated for describing variables that were dichotomous or

polytomous in nature. Changes in laboratory values from baseline to follow up were calculated and the mean change in values was compared using t-tests.

Results

Baseline lab values of all subjects and by Group are found in Table 1. There was a significant difference between baseline ferritin and TSAT values. Group A had a higher baseline ferritin and TSAT values than Group B.

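### Ending participation for judged non-compliance, with no as-randomised analysis set, can selectively lose week-6 outcomes and bias the effect sizes

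*Protocol*

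**What the plan says.** Protocol, Study Endpoints for each subject, lists six ways in which a patient reaches an end. Item 1 is the clinic evaluation at about 6 weeks. Item 6 stands as an alternative to it: the patient is non-compliant and the investigator "judges this non-compliance is enough to significantly alter evaluation of the treatment". No threshold is given. The SAP repeats the item in its own endpoint list. Protocol, Early termination of study, also allows termination for non-compliance, with a telephone evaluation at that time if one can be arranged.

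A note to item 6 says that stopping the oral medication for intolerance is not non-compliance but a study outcome. It continues: "Patients discontinuing oral medication for adverse effects may qualify for repeat IV treatment".

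Protocol, Statistical Analyses, compares responders (CGI score 1 or 2) by Fisher's exact test and IRLS change by an unequal-variance t-test. It names no analysis set, gives no rule for a terminated patient, and does not use intolerance. The SAP's Statistical analysis section describes only laboratory summaries and comparisons. A note under SAP Table 4 substitutes the latest available value when week 6 is missing. SAP Methods reports that "21 patients were terminated or lost to follow-up", without a split by arm or reason; the table it points to has no number and is not among Tables 1 to 6.

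**The concern.** Compliance is observed after randomisation and can depend on treatment and on how the patient is doing. If judged non-compliance ends follow-up, and analysis then rests on those who have ratings, the arms are no longer the groups that were randomised.

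The rule is worded identically for both double-dummy arms, but it need not act identically. A patient in the IV arm who skips vitamin C has already received the iron under supervision. A patient in the oral arm who skips pills has not. On the trial's premise that iron treats RLS, removing pill-skippers would mainly remove under-treated patients from the oral arm. That would raise the apparent oral response and narrow the difference from IV iron.

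The protocol's rationale makes effect size the primary goal, so bias in a single arm's response rate matters even if nobody relies on the significance test.

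**Working it through.** **1. The plan's own figure.** Protocol, Sample Size, assumes that "about 80% responded to IV iron (about 1000mg dose) and 50% responded to standard oral iron treatment" and states: "These percentage outcomes require a sample size of 70 (35 with each treatment) to provide a power of >80% with alpha = 0.05". Allocation is 1:1; sidedness is not stated and no dropout allowance is given. With the unpooled normal approximation, two-sided alpha 0.05 and 80% power:

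n per arm = (1.960 + 0.842)² × (0.80×0.20 + 0.50×0.50) / 0.30² = 7.849 × 0.41 / 0.09 = 35.8, so 36 per arm.

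Power at 35 per arm = Φ(0.30/√(0.41/35) − 1.960) = 79.2%. The planned 70 is therefore reproduced to within two patients. The test actually planned is Fisher's exact; its exact two-sided power at 35 vs 35 is 69.2%. That is the baseline below.

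**2. What selective removal would do.** The documents give no non-compliance rate, so this is a range under assumptions: a share d of oral patients is removed, all of them non-responders, and the IV arm is complete at 80%. The apparent oral rate is 0.50/(1 − d), and the oral n is 35(1 − d), rounded.

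| d | Oral n | Apparent oral rate | Difference (points) | Exact Fisher power |
|---|---|---|---|---|
| 0 | 35 | 50.0% | 30.0 | 69% |
| 5% | 33 | 52.6% | 27.4 | 63% |
| 10% | 32 | 55.6% | 24.4 | 53% |
| 15% | 30 | 58.8% | 21.2 | 41% |
| 20% | 28 | 62.5% | 17.5 | 29% |

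For contrast, loss that is equal in both arms and unrelated to outcome leaves the difference at 30 points. Power is then 64% (10% loss) or 58% (20% loss).

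**3. What the reported counts show.** The number randomised per arm is not given. As an assumed base I take patients with baseline hemoglobin (SAP Table 1): 47 in Group A and 46 in Group B.

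- CGI (Table 4) is present for 38 and 34, so missing for 9/47 = 19% and 12/46 = 26%; Fisher p = 0.47.
- IRLS change (Table 6) is present for 37 and 36, so missing for 10/47 = 21% and 10/46 = 22%; p = 1.0.

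The CGI gap, 9 + 12 = 21, equals the 21 terminated or lost. That is consistent with leavers having no CGI, but does not prove it.

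**4. Limits of those counts.** They count any follow-up value, not only week 6. Table 6 lists 2 + 4 + 5 = 11 IRLS values from weeks 1 to 4 and 61 from week 6. Against 93 with baseline hemoglobin, 93 − 61 = 32 have no listed week-6 IRLS, and these are not split by arm. Table 6 is also inconsistent: total 74, groups 37 + 36 = 73, time points 72. The groups are not identified; Group A looks like the IV arm from its mean ferritin rise (200.3 vs 23.3), which is an inference.

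**The case against.** A reader might infer that poor oral outcomes do drop out of the comparison. The documents do not support that.

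- Intolerance is exempt from item 6. An intolerant patient can stay to week 6, and a CGI above 2 then counts as non-response.
- The protocol's section on RLS clinical evaluations takes CGI-2 and IRLS by telephone as well as in clinic, so a termination call can yield ratings. The SAP note carries the last value forward.
- Item 6 does not say that removal precedes week 6, and the only planned pill count is at the 6-week visit.
- Both arms take pills, and the SAP says investigators were blind. Infusion reactions can remove IV patients as well.
- The SAP attributes some terminations to the pandemic and to the hiatus after the principal investigator's death.
- The protocol calls the between-arm comparison tertiary and does not regard its power figures as accurate.

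Much of this stands, and it rules out any claim that bias occurred. It does not remove the defect. The exemption covers item 6 only; adverse events and patient decision (items 3 and 4) also end participation. The carry-forward note sits in a SAP that already reports results, so it is not shown to be prespecified. SAP Methods says CGI was taken only at week 6, which conflicts with the protocol and with Table 4's footnote. Blinding stops the judgement being steered by knowledge of arm; it does not make the same judgement have the same effect in both arms.

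A second tempting reading is that oral patients were rated after IV iron while counted as oral. The note to item 6 gives no timing, but Protocol Study Design and Subject schedule, and SAP Methods, place the repeat treatment at 6 weeks. The passages need reconciling; they do not show contaminated ratings.

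**Conclusion.** The concern holds as a defect of the plan, not as a demonstrated bias. A discretionary post-randomisation rule without a threshold can end follow-up before or in place of the week-6 rating, and no as-randomised analysis set guards against it. Selective loss is possible, and the documents do not let it be checked by arm and reason.

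The likely direction, towards a flattered oral arm, rests on the trial's premise that iron treats RLS. The reported counts neither show one-sided loss nor exclude it; they are small and rest on an assumed base.

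The range of 63% to 29% power, against 69%, assumes that 5% to 20% of oral patients are removed, that all are non-responders, and that the IV arm is complete. It shows how sensitive the comparison is and is not an estimate of what occurred. The 21 losses are about 21% of the 100 implied by 70 planned plus 30 added, and cannot be read as 21 non-compliers.

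**What to change.** 1. Separate stopping study pills from stopping follow-up. Obtain the week-6 CGI and IRLS from every randomised patient whatever the compliance.
2. State that all randomised patients are analysed as assigned. Any compliance-based analysis is secondary.
3. List the 21 terminations or losses by arm and reason, and give the numbers randomised per arm.
4. For ratings already lost, add a sensitivity analysis that counts patients without a week-6 CGI as non-responders in both arms. It cannot be computed from the SAP, because Table 4 gives CGI means and medians but no responder counts.
5. Report stopping pills for intolerance by arm, since the protocol calls it an outcome. Do not impose it as non-response in the primary comparison: under double-dummy that would fail IV patients who had all their iron but stopped vitamin C, and applying it to the oral arm alone would favour IV by construction.
6. Reconcile the sentence on repeat IV treatment after oral discontinuation with the 6-week timing given elsewhere in both documents.

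The cost is one protocol sentence, one analysis rule, a listing from existing records and one extra analysis. Ratings never taken cannot be recovered, so step 1 now serves mainly the protocol text and any successor trial. Analysis as assigned will include the effect of real compliance on the oral arm.

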Our major problem in testing the treatment benefits for IDA-RLS for either oral or IV iron is that we do not know the actual effect size of either treatment. We have as an initial estimates the effect sizes from clinical experience with oral and IV iron treatment of IDA-RLS. These have to be considered as provisional estimates of effect sizes. Thus, although we have set the sample size to give adequate power to differentiate iv from oral iron treatment assuming these effect sizes, we do not consider the power estimates to be accurate. We feel they give us an adequate sample to establish effect sizes for future studies and to explore possible differential efficacy for the two treatments. The primary goal of the study is, therefore, to assess effect size. Evaluating differences between the treatments is a tertiary goal of this study.

The decision not to do a placebo control is based on the assumption that the treatment effect size can be adequately determined without a placebo. The decision to do a blinded comparator trial is based on the assumption that we will see differences between the treatments that will establish both the effect sizes and the procedures for a larger study to show these differences. We feel it is very important to determine if efficacy of these treatments differ for RLS-IDA in order to develop guidelines for future treatment of this clinically significant condition affecting many with IDA. We have assumed IV iron will be the preferred treatment for RLS-IDA, but we need to first evaluate this in this pilot study and then in a larger adequately powered clinical study.

Drugs used: The treatment doses are those accepted for treatment of RLS and also appropriate for treatment of RLS-IDA. Choosing doses equivalent to those for the treatment of RLS without IDA will allow a comparison with that literature. We will therefore use for oral iron ferrous sulfate 325 mg taken twice a day matching the dose used in the study of oral iron treatment for RLS without anemia [7]. For IV iron we will use ferumoxytol two doses of 510 mg spaced 2 to 7 days apart. This is the FDA approved dose for treatment of IDA with end stage renal disease. This dose matches the iron dosing used in the study of IV iron treatment for RLS without anemia [6], except we will use ferumoxytol provided by the sponsor rather than ferric carboxymaltose used in the prior trial.

Study Design

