The study is a randomized, comparative open label study to evaluate effect size and time course of treatment response for RLS-IAD over 6 weeks with a 46-week follow-up extension. Two medications and placebos will be used with equal random assignment to both groups

- Ferumoxytol intravenous (IV) 1020 mg – 2 vials of 510 mg (IV push, 2-3 mins) each given 2-7 days apart
- Ferrous sulfate 325 mg (oral) tabs morning and evening.
- Placebo: oral vitamin C 500 mg tabs, Saline infusion

Primary outcome is the CGI-2 score at 6 weeks after treatment starts. IV ferumoxytol 1020 mg treatment (2 separate doses 510 mg 2-7 days apart) will be offered to those not significantly responding (CGI-2 scores less than much or very much improved) at 6 weeks after oral-iron treatment and still meeting all requirements for entry to study. All responders will be followed for 12 months after treatment.

Study Objectives

Primary objectives

1. Determine relative effect sizes of standard IV and oral iron treatment of RLS with iron deficiency anemia for the PGI-2/CGI-2 (much and very much improved) and for IRLS scores
2. Determine time course of treatment response for IRLS, PGI-1 and PGI-2 scores

Secondary objectives

1. Estimate survival times for effective treatment (no return to other RLS medications) for 1 year after treatment
2. Evaluate possible predictors of treatment response
 - a. Iron status or iron response
 - b. IRLS severity
 - c. Subject characteristics (age, gender)
 - d. Medical factors affecting iron status

Tertiary/exploratory objectives

1. Evaluate significance of efficacy differences if any between oral and IV iron treatments at 6 weeks after treatment: Hierarchical testing first for the percentage with CGI-2 of much or very much improved and second for change from baseline in the IRLS score.
2. Evaluate efficacy benefits of each treatment for usual outcomes related to RLS morbidity: sleep, fatigue, quality of life, and mood.
3. Compare lymphocytes of RLS-IAD and non RLS-IAD for differences in iron related proteins.

Study Procedures

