Change in hemoglobin and iron parameters for all subjects and by group are shown in Table 3. The mean change in hemoglobin from baseline to follow up was 1.2 (SD 1.3) for Group A and 6.0 (17.2) for Group B. The mean change in Ferritin from baseline to follow up was 200.3 and 23.3 for Group A and Group B, respectively. The mean change in TSAT from baseline to follow up was 16.5 and 12.2 for Group A and Group B, respectively. The mean change in MCV from baseline to follow up was 24.2 and -17.6 for Group A and Group B, respectively. There was a significant difference between follow up ferritin and TSAT values. Group A had a higher follow up ferritin values ($p=0. <0.0001$) and higher TSAT ($p=0.007$) values compared to Group B.

Table 4 shows the changes in patient severity scores from baseline to follow up, and the follow up patient and clinical global impression scores for all subjects and by group. No significant differences between the 2 groups in terms of change in (1) patient severity score from baseline to follow up, (2) follow up patient global impression score, or (3) clinical global impression score were observed.

Table 5 shows the change in FSS from baseline to follow up. There were no significant differences between the 2 groups in terms of change in FSS.

Table 6 shows the change in IRLS score from baseline to follow up for all subjects and by group. Group B had a greater reduction in IRLS score from baseline to follow up compared to Group A

NOT SURE IF/HOW YOU WANT TO PRESENT THE ADVERSE REACTION DATA

Commented [VS1]: These are results from my original analysis. I still need to double check the results. However, before doing so, I want to confirm that there are no new data to analyze.

Commented [VS2]: Will define "Group A" and "Group B" once I know which group is which

TABLES**Table 1. Baseline hemoglobin and iron parameters for all subjects and by group.**

	Total	Group A	Group B	P-value¹
Hemoglobin	N=93	N=47	N=46	0.14
Mean (SD)	11.1 (1.5)	11.3 (1.3)	10.8 (1.6)	
Median (IQR)	11.6 (10.2, 12.2)	11.7 (10.8, 12.3)	11.6 (9.7, 12.1)	
Min, Max	7.0, 13.1	7.2, 13.1	7.0, 13.0	
Ferritin	N=91	N=45	N=46	0.017
Mean (SD)	17.9 (16.7)	22.6 (19.6)	13.5 (12.1)	
Median (IQR)	11.0 (7, 24)	19 (7, 29)	10.0 (7-15)	
Min-Max	3, 102	4, 102	3.0, 59.0	
TSAT	N=92	N=46	N=46	0.025
Mean (SD)	10.4 (6.2)	11.4 (5.9)	9.5 (6.5)	
Median (IQR)	9.0 (6, 13)	10.0 (8, 15)	8.5 (6.0-11.0)	
Min-Max	2, 36	2, 36	2, 32	
MCV	N=93	N=47	N=46	0.233

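### The primary objective is the relative effect size of IV and oral iron, but no between-arm estimate or confidence interval is planned or reported, and CGI responder counts are missing

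*Protocol*

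**What the plan says.** The Protocol, under Study Objectives, lists as primary objective 1: "Determine relative effect sizes of standard IV and oral iron treatment of RLS with iron deficiency anemia for the PGI-2/CGI-2". The objective takes the top two improvement categories as response, and it covers the IRLS as well. The rationale says "The primary goal of the study is, therefore, to assess effect size", and of the sample-size assumptions, "We feel they give us an adequate sample to establish effect sizes for future studies". It also says "Evaluating differences between the treatments is a tertiary goal of this study". The tertiary objective concerns the significance of any efficacy difference, tested hierarchically.

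Protocol, Statistical Analyses, plans the effect size by arm: "The percentage responding will be evaluated for each drug condition to determine overall effect size at 6 weeks after treatment". CGI response is a score of 1 or 2; IRLS and PGI are taken as change from baseline. Between arms, the 6-week outcomes are to be "compared using a standard unpaired unequal variance t-test for the change in IRLS scores from baseline". For the binary outcome the same section plans an exact test: "The number of responders compared to no-responders will be compared using the Fisher Exact test".

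The SAP makes CGI-I and IRLS change co-primary. Its Statistical analysis section describes summaries and t-tests for laboratory values and names no efficacy estimator. Tables 4 to 6 give N, mean (SD), median (IQR), range and a Kruskal-Wallis p-value. The Results say "No significant differences between the 2 groups in terms of change in (1) patient severity score from baseline to follow up", nor in the follow-up patient and clinical global scores. The same is said of FSS. IRLS is reported as a greater reduction in Group B.

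**The concern.** The objectives rank estimation above testing, while the plan and tables deliver a test and leave the estimate out. A per-arm mean with its SD is not a relative effect size, and a p-value does not show which differences remain compatible with the data. A pilot meant to supply effect sizes for a later trial needs the difference between arms and its precision.

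Two consequences follow. First, the responder outcome, which heads the protocol's hierarchy and drives its sample size, has no reported count in either arm. Second, outcomes with similar observed effects are described differently according to which side of 0.05 the p-value falls. For IRLS, the tables also use a rank test in place of the planned Welch test, whose companion interval is the missing estimate.

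**Working it through.** **1. The plan's own figure.** Inputs from Protocol, Sample Size: 80% versus 50%, alpha 0.05 (two-sided assumed), 35 per arm. Unpooled normal formula: n = (1.96 + 0.842)² × (0.80×0.20 + 0.50×0.50) / 0.30² = 35.8, so 36 per arm or 72 in total. Power at 35 per arm is 79.2%. This is close to the stated 70 patients and 80%. The same inputs give the precision, which the protocol does not state: SE = √(0.41/35) = 0.108, so 30 ± 21 points.

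**2. Differences from the printed summaries (SAP Tables 4 to 6).** Difference = mean A − mean B; SE = √(s_A²/n_A + s_B²/n_B); Welch degrees of freedom; 95% CI = difference ± t × SE. For IRLS, 7.7²/37 = 1.602 and 9.5²/36 = 2.507, so SE = √4.109 = 2.027. With df 67.3 and t = 1.996, the half-width is 4.05.

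| Outcome | A: mean (SD), n | B: mean (SD), n | A − B | 95% CI | Printed p |
|---|---|---|---|---|---|
| IRLS change | -8 (7.7), 37 | -12.2 (9.5), 36 | 4.2 | 0.15 to 8.25 | 0.047 |
| FSS change | -7.8 (14.2), 32 | -14.3 (14.5), 29 | 6.5 | -0.87 to 13.87 | 0.11 |
| PGI severity change | -1.7 (1.8), 30 | -2.1 (1.9), 27 | 0.4 | -0.59 to 1.39 | 0.24 |
| PGI at follow-up | 2.1 (1.1), 40 | 2.1 (1.2), 37 | 0.0 | -0.52 to 0.52 | .72 |
| CGI at follow-up | 2.1 (1.2), 38 | 2.1 (1.4), 34 | 0.0 | -0.62 to 0.62 | .80 |

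For the change scores, a positive difference means a smaller reduction in A. Dividing by the pooled SD gives 4.2/8.63 = 0.49 for IRLS and 6.5/14.34 = 0.45 for FSS.

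**3. CGI responders.** Table 4 gives medians of 2 (A) and 1.5 (B), each with IQR 1 to 3. A median of 2 or less puts at least half of each arm at a score of 1 or 2. An upper quartile of 3 puts at most about 28/38 or 25/34 there, or 74% in each arm. The counts themselves, and so the risk difference, cannot be recovered.

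To show the precision, assume the same rate in both arms and combine the Wilson limits by Newcombe's method. At 50%, the Wilson limits are 0.348 to 0.652 (n = 38) and 0.341 to 0.659 (n = 34), so the half-width is √(0.152² + 0.159²) = 0.22. At 74% the interval is -0.196 to 0.201. That is about ±20 to 22 points across the range, against a planning difference of 30. At 90% it would be about ±15, so the figure does not apply to every rate.

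**The case against.** The best defence is that the protocol calls differences between treatments a tertiary goal, speaks of the effect size of either treatment, and plans per-arm estimates accordingly. It also says its power estimates should not be considered accurate. The tables print means, SDs and Ns, so a reader can derive intervals for the continuous outcomes, as is done here. The SAP's comments show that its results are still to be checked.

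Part of this stands: the continuous differences are recoverable, and the gap is one of planning and reporting. But what the objectives rank as tertiary is the significance of differences; relative effect size is listed separately as primary. Even on a per-arm reading, no interval is planned for either arm. The responder counts are not recoverable at all.

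Three stronger readings are tempting and not supported.
- A reader might infer that the SAP claims the treatments are equal. It does not: its wording is about significance, and it reports IRLS as favouring B.
- A reader might suspect that A's IRLS mean, printed as -8, hides a value such as -8.4 that would carry the interval across zero. With the 73 patients in the arms, -8.4 implies a total of (37×(-8.4) + 36×(-12.2))/73 = -10.3, whereas -8.0 gives the printed -10.1.
- A reader might size the next trial from the ends of the planning interval. Those sizes would rest on hypothetical response rates, not trial data.

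**Conclusion.** The point holds as an omission that should be corrected: following the plan as written does not deliver primary objective 1. No between-arm estimate or interval is planned or reported, and the responder result is absent. FSS, with a standardised difference of 0.45, remains compatible with anything from a trivial difference in A's favour to 13.87 points in B's. IRLS, at 0.49, has an interval that only just excludes zero.

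The figures rest on rounded summaries. Tables 4 and 6 include follow-up before week 6, which the intervals treat as 6-week data. Table 6 shows a total of 74, arms summing to 73 and a footnote summing to 72. The responder half-width assumes equal rates of 50% to 74%. Groups A and B are not decoded; the larger ferritin rise in A (200.3 versus 23.3) suggests that A is IV iron, but that is an inference and nothing above depends on it.

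**What to change.** In Protocol, Statistical Analyses, and in the SAP's Statistical analysis section and Tables 4 to 6:

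- Report the number and percentage of CGI responders (score 1 or 2) by arm, with the risk difference and its 95% CI. Newcombe's interval is one suitable choice. Keep the Fisher test as planned.
- Report the mean difference in IRLS change with its Welch 95% CI, in line with the protocol's planned method, and do the same for PGI severity change and FSS change.
- Describe non-significant results by their estimates and intervals, stating which differences remain compatible with the data.

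Apply this to every listed comparison, not only to selected ones. It needs no new data: a few lines of code and some table columns. The one real cost is that the text will show how imprecise the estimates are.
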